3.14. Study Procedures and Assessments

Study procedures and assessments with their time points are summarized in Table 1. Detailed by-visit information is provided starting with Section 3.14.1. Detailed descriptions of each assessment are provided in Section 6 (pharmacokinetic and pharmacodynamic assessments), Section 7 (safety assessments), and Section 8 (biomarker and pharmacogenetic assessments).

Table 1: Study Procedures and Assessments

Time period	Up to 8 weeks to 2 weeks before Visit 2	Up to 4 weeks					
Visit number	Visit 1	Visit 2		Visit 3			Visit 4
Procedures and assessments	Screening ^a	Day -1 (first admission)	Day 1	Day -1 (second admission)	Day 1	Day 2	Follow-up ^b
Informed consent	X						
^c Medical history	X	X					
^d Prior medication history	X	X					
Inclusion and exclusion criteria	X	X					
Clinical laboratory tests (hematology, serum chemistry, urinalysis)	X	X		X			X
Coagulation test	X						
^e Corticoid plasma levels				X		X	
^f Virology	X						
Urine drug screen	X	X		X			
^g Physical examination	X	X		X			X
^h Modified Allen test	X						
UHDRS-TMS (HD patients only)	X	X	X	X	X		
ⁱ 12-lead standard ECG	X	X	X	X	X	X	X
^j Vital signs measurement	X	X	X	X	X	X	X
C-SSRS (screening version)	X						
^k Pridopidine administration						X	
^l (S)-(-)-[¹⁸ F]fluspidine or [¹⁸ F]fallypride administration			X		X		
^m Screening T1 MPRAGE 3D MRI	X						
ⁿ PET scan for test-retest cohort			X		X		
^o PET session 1			X				
^p PET session 2					X		

Time period	Up to 8 weeks to 2 weeks before Visit 2	Up to 4 weeks					
Visit number	Visit 1	Visit 2		Visit 3			Visit 4
Procedures and assessments	Screening ^a	Day -1 (first admission)	Day 1	Day -1 (second admission)	Day 1	Day 2	Follow-up ^b
MR-AC, T1 MPRAGE 3D MRI, ASL, 2DMRS, rs-fMRI			X ^d		X ^p		
Blood samples for radioactivity levels ^r			X		X		
Blood samples for PK analyses ^s					X	X	
Blood samples for PD biomarker analysis ^t				X	X	X	
Genotyping for CYP2D6 and exploratory ^u	X						
Monitoring of adverse events ^v	X	X	X	X	X	X	X
Concomitant medication ^w	X	X	X	X	X	X	X
Check of study compliance		X		X			

^a The screening procedures can be performed over several days as long as they are completed within the defined visit window. During screening, subjects will be informed of study restrictions and compliance requirements.

^b The follow-up visit will take place 6 days after the visit 3 dose (± 1 day).

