^c Events that occurred prior to the signing of the informed consent form will be recorded in the medical history.

^d Medications administered prior to any study drug administration will be recorded as prior medications.

^e Corticoid plasma levels, to be taken directly prior to tracer dosing (DHEA, progesterone, testosterone, cortisol, where feasible also androstanolone, allopregnanolone, pregnenolone).

^f Virology testing will include: human immunodeficiency virus (HIV-1, HIV 2), HBsAg, and/or hepatitis C.

^g Height, weight, and body mass index will be measured only at screening. Complete physical examination on screening and follow up/early termination visits only. On other occasions, abbreviated/symptom- oriented physical examination will be conducted.

^h Part 0 and Part A subjects only.

ⁱ The 12-lead ECG is to be performed before pridopidine administration; immediately before administration of the tracer (approximately 90 minutes after pridopidine administration), and at the end of the first PET scan (approximately 3.5 hours after pridopidine administration). When ECG collection coincides with a pharmacokinetic sample, ECG will be collected before the pharmacokinetic sample.

^j Vital signs (pulse, respiratory rate, body temperature, and systolic and diastolic BP) will be measured with the subject seated or supine immediately prior to administration of pridopidine, and prior to and immediately after each PET scan. BP will be measured in the same arm throughout the study, whenever possible. When vital signs collection coincides with PK sample, vital signs will be collected before the PK sample.

^k Except for test-retest cohort (Part 0).

^l [¹⁸F]fluspidine for Parts A and 0, [¹⁸F]fallypride administration for Part B.

^m This should be performed as the final procedure of the screening visit, after all other eligibility criteria have been fulfilled.

ⁿ For the test-retest cohort, fluspidine will be administered twice. The 2 tracer doses will be administered separately within a certain time frame, without pridopidine. The PET session 2 will take place at approximately a similar time of day (± 1 hour) as the baseline PET session 1, on another day (at least 24 hours ~ 10 half-lives ^{18}F apart).

^o In an effort to facilitate easier PET procedure for HD patients, after the first 90-minute PET acquisition block, the subsequent 30-minute PET acquisition blocks are made optional per Investigator's judgement (refer to study Imaging Manual for details).

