3.14.2. Visit 2 (PET Session 1)

Subjects who meet the inclusion and exclusion criteria at visit 1 will continue to visit 2.

Subjects who continue to meet the inclusion and exclusion criteria will be assigned a permanent unique treatment number. This assigned number will be entered in the CRF.

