3.14.2.1. Visit 2, Day -1

The following procedures will be performed at visit 2, day -1:

- review of medical history
- review of prior medication history
- review inclusion and exclusion criteria
- clinical laboratory testing (hematology, serum chemistry, and urinalysis)
- urine drug screen
- abbreviated/symptom-oriented physical examination
- UHDRS-TMS (HD patients only)
- 12-lead standard ECG
- vital signs measurements
- inquire about adverse events
- review of concomitant medication
- review study compliance

3.14.2.2. Visit 2, Day 1

The following procedures will be performed at visit 2, day 1:

- corticoid plasma level measurements
- UHDRS-TMS (HD patients only)
- 12-lead standard ECG
- vital signs measurements
- $[^{18}\text{F}]$ fluspidine (Parts A and 0) or $[^{18}\text{F}]$ fallypride (Part B) administration – refer to study Imaging Manual for details

- PET scan (session 1) - refer to study Imaging Manual for details
- MR-AC, T1 MPRAGE 3D, ASL, 2DMRS, and rs-fMRI – refer to study Imaging Manual for details
- collect blood samples for measurement of radioactivity levels (excluding Part B subjects) – refer to study Imaging Manual for details
- inquire about adverse events
- review of concomitant medication

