3.14.3. Visit 3 (PET Session 2)

3.14.3.1. Visit 3, Day -1

The following procedures will be performed at visit 3, day -1:

- clinical laboratory testing (hematology, serum chemistry, and urinalysis)
- urine drug screen
- abbreviated/symptom-oriented physical examination
- UHDRS-TMS (HD patients only)
- 12-lead standard ECG
- vital signs measurements
- inquire about adverse events
- review of concomitant medication
- review study compliance
- collection of blood for exploratory pharmacodynamic biomarker analysis

3.14.3.2. Visit 3, Day 1

The following procedures/assessments will be performed at visit 3, day 1:

- corticoid plasma level measurements
- UHDRS-TMS (HD patients only)
- 12-lead standard ECG
- vital sign measurements
- pridopidine administration
- $[^{18}\text{F}]$ fluspidine (Parts A and 0) or $[^{18}\text{F}]$ fallypride (Part B) administration – refer to study Imaging Manual for details
- PET scan (session 2) – refer to study Imaging Manual for details
- MR-AC, T1 MPRAGE 3D, ASL, 2DMRS, and rs-fMRI – refer to study Imaging Manual for details

- collect blood samples for measurement of radioactivity levels (excluding Part B subjects) – refer to study Imaging Manual for details
- collect blood samples for pharmacokinetic analyses (predose and up to 12 hours after dosing)
- collect blood samples for exploratory pharmacodynamic biomarker analysis (predose and 4 and 8 hours postdose)
- monitoring of adverse events
- review of concomitant medication

3.14.3.3. Visit 3, Day 2

The following procedures/assessments will be performed at visit 3, day 2:

- 12-lead standard ECG
- vital signs measurements
- collect blood samples for pharmacokinetic analyses (24 hours postdose)
- collect blood samples for exploratory pharmacodynamic biomarker analysis (24 hours postdose)
- monitoring of adverse events
- review of concomitant medications

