4.2. Subject Exclusion Criteria

Subjects will not be enrolled in this study if they meet any of the following criteria:

Healthy Subjects:

- a. CYP2D6 poor metabolizers
- b. The subject has been previously exposed to ionizing radiation or radioactive substances as a result of clinical research or medical treatment in the past 10 years.
- c. The subject has large scale tattoos, in particular involving the head and neck area.
- d. The subject has a contraindication to having an MRI, including (but not limited to):
 - The presence of metal implants (excluding metal dental crowns) that could affect MRI imaging OR

- has worked with ferrous metals either as a vocation or hobby (for example sheet metal worker, welder or machinist) in such a way that might have led to unknown indwelling of metal fragments that could cause injury if moved in response to the magnetic fields during the MRI imaging.
- e. The subject suffers from claustrophobia or needle phobia.
- f. The subject has a finding on screening MRI that will, in the opinion of the PI impair the safety of the subject or the scientific integrity of the study.
- g. The subject has a known coagulation abnormality.
- h. Parts A and 0 only: Individuals who had evidence of only one patent arterial supply to the hand (modified Allen test).
- i. Any current or history of heart condition or increased pro-arrhythmic risk, including:
 - History of cardiovascular disease (eg, coronary artery disease, stroke, arrhythmias, congestive heart failure, uncontrolled hypertension, deep vein thrombosis, pulmonary embolism, family history of thrombophilia)
 - History of Long QT Syndrome or a first degree relative with this condition
 - Family history of sudden death/Brugada syndrome
 - A prolonged Fridericia-corrected QT (QTcF) interval (defined as a QTcF interval of >450 msec) at the screening or admission (baseline) visit(s). If there is evidence of a prolonged QTcF interval from the initial (single) measurement, then the ECG can be repeated twice, and the mean of the 3 screening measurements will be used to determine whether or not the subject is suitable for inclusion in the study.
 - Any repolarization deficits
 - Untreated hypokalemia and/or untreated hypomagnesaemia
 - Unclear syncopes
 - Any other clinically significant abnormal ECG as judged by the investigator.

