- j. A prolonged QTcF interval (defined as a QTcF interval of >450 msec) at the screening visit. If there is evidence of a prolonged QTcF interval at screening from the initial (single) measurement, then the ECG will be repeated twice, and the mean of the 3 screening measurements will be used to determine whether or not the patient is suitable for inclusion in the study.
- k. Patients with clinically significant heart disease at the screening visit, defined as follows: (i) significant cardiac event (eg, myocardial infarction), angina pectoris or episode of congestive heart failure with symptoms >Grade 2 New York Heart Association classification within 12 weeks before first admission, or presence of cardiac disease that in the opinion of the investigator increased the risk of ventricular arrhythmia, (ii) history of arrhythmia (multifocal premature ventricular contractions, bigeminy, trigeminy, ventricular tachycardia) that was symptomatic or required treatment (Common Terminology Criteria for Adverse Events Grade 3), symptomatic or uncontrolled atrial fibrillation despite treatment, or asymptomatic sustained ventricular tachycardia, (iii) presence of left bundle branch block, (iv) history of deep vein thrombosis or pulmonary embolism, and/or (v) family history of thrombophilia.
- l. Patients with a known history of Long QT Syndrome or a first degree relative with this condition.
- m. Patients with a history of epilepsy or of seizures within the last 5 years.

- n. Have other serious medical illnesses (including but not limited to uncontrolled hypertension, respiratory disease including severe form of asthma, hepatic disease, renal disease, AIDS, unstable psychiatric or other neurologic disorder, endocrine [including controlled diabetes], gastrointestinal, and metabolic diseases) which in the opinion of the investigator may put the patient at risk when participating in the study or may influence the results of the study or affect the patient's ability to take part in the study.
- o. Patients with serum potassium, magnesium and/or calcium levels outside of the central laboratory's reference range at the screening visit and considered clinically significantly abnormal by the investigator. Repeat testing is allowed (up to a maximum of 3 tests) if required to establish whether values are within normal range or clinically significantly abnormal.

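### The 450 msec QTcF limit applies to Huntington's disease patients at screening only, but to healthy subjects at screening or admission

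*Protocol*

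**What the plan says.** Protocol Section 4.2 has separate exclusion lists for the two populations, and the synopsis repeats both.

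- HD patients, criterion j: "A prolonged QTcF interval (defined as a QTcF interval of >450 msec) at the screening visit". If the first reading is prolonged, the ECG is repeated twice and the mean of the three screening readings decides.
- Healthy subjects, criterion i: "defined as a QTcF interval of >450 msec) at the screening or admission (baseline) visit(s". Two further recordings are optional after a prolonged reading. The deciding rule is this: "the mean of the 3 screening measurements will be used to determine whether or not the subject is suitable for inclusion in the study".

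Eligibility is looked at again on Visit 2 day -1. Section 3.14.2.1 lists "review inclusion and exclusion criteria" alongside an ECG, and Section 3.14.2 adds: "Subjects who continue to meet the inclusion and exclusion criteria will be assigned a permanent unique treatment number". Visit 3 has its own admission, headed "Day -1 (second admission" in Protocol Table 1. Section 3.14.3.1 lists a "12-lead standard ECG" for that day but no criteria review. On Visit 3 day 1, Table 1 footnote i says: "The 12-lead ECG is to be performed before pridopidine administration".

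Section 9.1 allows up to 4 HD patients, as an option. Section 5.1.1 allows them up to 112.5 mg, against 90 mg in healthy subjects.

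**The concern.** The limit is the same number in both populations, so the difference is not a higher tolerance for HD patients. It is a difference in which ECGs count. For an HD patient, only the oldest ECG before dosing is held against 450 msec. Whether a prolonged admission reading stops him is left to judgement.

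The HD list is also thinner on judgement. Healthy criterion i includes repolarization deficits and any other ECG abnormality that the investigator considers clinically significant. The HD list has no direct counterpart. The nearest are k (heart disease at screening) and n (other serious illness).

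A smaller problem sits in the healthy list. An admission reading can trigger the repeat rule, but the rule then decides on screening readings. It cannot be followed literally in that case.

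What is at stake is patient safety on a small scale. No endpoint or analysis is affected.

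**Working it through.** The plan states no figure to reproduce. The check compares the texts and then counts ECGs.

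**1. Which pre-dose ECGs carry the 450 msec limit** (visits from Protocol Table 1, limits from Section 4.2)

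| ECG | Healthy | HD |
|---|---|---|
| Screening | yes | yes |
| Visit 2 day -1 (first admission) | yes | no |
| Visit 2 day 1 | no | no |
| Visit 3 day -1 (second admission) | only if admission covers both visits | no |
| Visit 3 day 1, before pridopidine | no | no |

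**2. Does another rule fill the gap?** The Visit 2 day -1 review applies the criteria as written. Criterion j refers only to screening, so an HD patient still satisfies it whatever that day's ECG shows. No numeric QTcF limit appears in Protocol Sections 3.12 (stopping), 3.14.3 (Visit 3), 4.4 and 7.1.7 (withdrawal) or 7.6 (ECG). SAP Section 7.7 gives descriptive summaries and normal/abnormal shifts. SAP Tables 1 and 2 cover laboratory values and vital signs. Post-screening numeric limits found for HD patients: 0.

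**3. Size of the difference from healthy subjects**, with up to 4 HD patients (Section 9.1)

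- Admission means Visit 2 only: 4 patients × 1 ECG = at most 4.
- Admission means both visits: 4 patients × 2 ECGs = at most 8.

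The plural ending in criterion i and the label of the second admission in Table 1 favour 8. Elsewhere the protocol defines baseline as Visit 2 day -1 (for example HD exclusions p and q), and SAP Section 7.7 takes Visit 2 as the ECG baseline; these favour 4. With no HD cohort the count is 0. Section 9.1 lets cohort sizes change, and the count scales at 1 to 2 ECGs per patient. The day 1 ECGs are left out because neither population has a limit there.

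**4. Age of the only ECG with a limit**

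- At Visit 2: 2 to 8 weeks (Section 3.14.1).
- At dosing, minimum: 2 weeks, since Visit 3 follows Visit 2.
- At dosing, maximum: 8 weeks if the screening window in Section 3.1 is counted back from pridopidine. Otherwise, assuming the 4-week study period runs from Visit 2 through follow-up as Table 1 sets it out, and with follow-up 6 ± 1 days after the dose (Section 3.14.4): 56 + 28 − 7 = 77 days to 56 + 28 − 5 = 79 days, or 11.0 to 11.3 weeks.

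**5. Repeat rules.** In HD criterion j, trigger and average both refer to screening, so the rule is consistent. In healthy criterion i the trigger includes admission but the average does not. SAP Section 7.7 already averages repeated ECGs within a visit, which is the natural repair.

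**The case against.** The best case for the plan is that screening-only was intended and that other safeguards carry the weight.

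On intent, j refers to screening throughout, and HD criteria k, o, r and s are tied to screening too. The HD list also departs knowingly from the healthy one elsewhere, for example on creatinine clearance (60 against 90 mL/min). The risk text, the dose justification and part of Section 4.3 are redacted, and the safety monitoring plan is not available. A reason may exist there. This stands as a possibility only: nothing visible gives a reason, and HD criterion z does use admission visits for drug and alcohol tests, although those concern recent use.

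On safeguards, much stands:

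- A physician reads every ECG, and a clinically significant finding becomes an adverse event (Section 7.6).
- The investigator or sponsor can withdraw a patient at any time (Sections 3.12, 4.4, 7.1.7).
- HD criterion p bars QT-prolonging drugs for 6 weeks before Visit 2 day -1. The healthy look-back is 28 days before study drug.
- Serum chemistry, which includes potassium, magnesium and calcium (Protocol Table 5), is taken at screening and at both admissions.
- ECGs follow at about 90 minutes and 3.5 hours after the single supervised dose, on day 2 and at follow-up.
- Section 4.3 speaks generally of excluding subjects at increased pro-arrhythmic risk, and Section 1.4.4 regards the highest doses as safe and well tolerated.

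A reader might infer that HD patients go unmonitored after screening, or that the plan knowingly doses patients with prolonged QTcF. The documents support neither. ECGs are scheduled and read throughout; what is missing is a numeric limit. A reader might also treat every pre-dose HD ECG as part of the discrepancy. That overstates it, because healthy subjects have no limit on the day 1 ECGs either.

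Finally, a limit at Visit 3 is not properly an exclusion criterion: by then the patient is enrolled, numbered and scanned. That is correct, and the fix treats it as a dosing rule.

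**Conclusion.** The point holds as a cheap improvement. HD patients have no numeric QTcF criterion after screening, while healthy subjects have the same limit at one or two later visits. A confirmed admission QTcF above 450 msec fails a criterion in a healthy subject and fails no numeric criterion in an HD patient.

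The size is at most 4 or at most 8 ECGs, depending on what admission means in criterion i, in an optional cohort of up to 4. The documents give no QTcF distribution, so no probability of a prolonged admission reading can be stated. The wording difference is certain. The clinical consequence is small, given the remaining safeguards, and less certain because of the redactions. The repeat-rule wording in the healthy list is a separate, editorial defect that adds no weight to the HD point.

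**What to change.** 1. In HD exclusion j (Section 4.2 and synopsis), use the visit wording of healthy exclusion i, so that the limit applies at least at the Visit 2 day -1 criteria review.
2. In both lists, have the repeat rule average the three measurements from the visit at which the prolonged reading occurred. Once j is widened, its repeat rule needs this as much as the healthy one does.
3. Optionally, and for both populations alike, state in Section 3.14.3 as a dosing rule that pridopidine is withheld if the Visit 3 day -1 QTcF, confirmed by the mean of three, exceeds 450 msec.

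If screening-only was intended for HD patients, give the reason and say what happens to a later reading above 450 msec.

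The cost is wording, a check of ECGs already scheduled and an occasional pair of repeats. An HD patient may now and then be lost at admission. If that happens at Visit 3, he has already had the baseline tracer scan: up to 330 MBq × 22.1 µSv/MBq = 7.3 mSv with fluspidine (Section 1.4.2.2), or 220 MBq × 21.6 µSv/MBq = 4.75 mSv, stated as 4.8 mSv, with fallypride (Section 1.4.3.2). In Part A he has also had arterial cannulation.
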